## **1.4 Preliminary Data**

Dietary fibers modulated gut microbiota and conferred clinical benefits in PWS patients. Children aged 3-16 years old (N=17 with PWS and N=12 with simple obesity) were prescribed a diet enriched with wholegrains, traditional Chinese medicinal foods and prebiotics (WTP diet) for 30-90 days (5). This diet was specifically formulated to include a large amount of dietary fibers with diverse physicochemical structures to maximize carbohydrate fermentation by the gut microbiota. The diet induced significant and yet

similar shifts in the overall gut microbiota structure in both groups, an effect associated with improvements in metabolic parameters including body weight and glucose homeostasis (Figure 1). Importantly, based on a hyperphagia questionnaire, we observed a modest but non-significant improvement in the overall food-related behavior in PWS patients (P=0.074).

Our network analysis identified guild-level structure in the gut microbiota (Figure 2). When supplemented with dietary fiber, gut bacteria exhibited co-abundance patterns and formed genome interaction groups (GIGs) or "guilds" (an ecological group in which members exploit an environmental resource in a similar way and show co-abundant behavior). Three guilds, which included strains of beneficial bacteria such as Bifidobacterium were negatively correlated with body weight and HbA1c, while 9 guilds which contained many opportunistic pathogens such as LPS producers were positively associated with disease parameters. Taken together, we showed that high-fiber diet was a feasible and effective way to modulate gut microbiota in PWS patients, which conferred clinical improvements and may also alleviate hyperphagia.

[figure not shown]

Figure 2. Network analysis of the bacterial genomes. Genomes of the same color were grouped in the same guild. Size of the nodes indicated the abundance of genomes. Red and blue lines denoted positive and negative correlations respectively.

[figure not shown]
Interestingly, transplantation of the pre- and post-intervention gut microbiota from the same patient to germfree mice induced opposite responses in the recipient mice. While these mice had no genetic defects and were maintained on a standard chow diet, receiving the pre-intervention PWS gut microbiota alone was sufficient to induce inflammation, excessive fat accumulation and liver steatosis whereas the post-

HRP-503a - TEMPLATE - Interventional Research Protocol 1.1.21 Protocol Title: Gut microbiota and hyperphagia in PWS Protocol Version Date: October 7, 2022

intervention gut microbiota was without effect. This piece of causality evidence showed that at least some of the major metabolic phenotypes associated with PWS can be transferred to germ-free mice along with the transplanted gut microbiota (5, 15).

**Dietary fibers selectively** promoted acetate and butyrate producers and structured a healthier gut ecosystem. Patients with type 2 diabetes were randomized to receive either the high-fiber WTP diet (W group; N=27) or usual care (U group; N=16) for 84 days (16). We identified 141 bacterial genomes that had the genetic capacity for fermenting dietary fibers. Intriguingly, only 15 of them were able to take advantage of the fibers and increased their abundance, while 79 remained unchanged and 47 were suppressed during the high-fiber intervention. All 15 positive responders possessed the pathways to produce acetate, and some could also produce butyrate. When the gut microbiota was

dominated by these bacteria, there was a concomitant reduction in bacteria that produced metabolically detrimental compounds (e.g. LPS, hydrogen sulfide and indole) and collectively these microbial changes led to improved metabolic outcomes (Figure 3). Acetate and butyrate can stimulate the production of GLP-1 and PYY; LPS can induce systemic inflammation; indole and hydrogen sulfide can inhibit the production of GLP-1 and PYY (17, 18). Shifting of the abundance of producers of these bioactive compounds may drive the improvement of metabolic phenotypes. It would be interesting to assess if appetite regulation and feeding behavior are also modulated by these high fermentable fiber-induced changes in gut microbiota.

## 1.5 Sample Size Justification

No power calculation is performed for this pilot study. We aim to recruit 10 patients with hyperphagia(5 male and 5 female) to capture a reasonable degree of variations in gut microbiota composition.

## 1.6 Study Variables

## A. Independent Variables, Interventions, or Predictor Variables NBT-NM108

## **B.** Dependent Variables or Outcome Measures

Gut microbiota composition, weight, fMRI, total caloric intake, hyperphagia behavior, physical activity behavior and hormones of satiety

## 1.7 Drugs/Devices/Biologics

HRP-503a - TEMPLATE - Interventional Research Protocol 1.1.21 Protocol Title: Gut microbiota and hyperphagia in PWS Protocol Version Date: October 7, 2022

## A. Schedule and Administration

Participants will receive NBT-NM108 prepared as muffin (each contains 30 g of the product) for 4 weeks. The dosage will be 2 muffins a day. This dosage of NBT-NM108 will provide 24 g/day of dietary fibers of diverse physicochemical structures as sources of fermentable carbohydrates for the gut microbiota. Participants will be given a supplement diary to keep track of consumption of muffins along with potential side effects (**Appendix H**).

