## ELIGIBILITY SCREENING.

For recruitment, individuals with patients with hyperphagia will be identified via [name] RWJMS clinic and DEEP6. Patients identified on the DEEP6 list will be considered for the study if they are patients of [name]. Once identified, the research staff in Rutgers will contact the patient and guardian via a phone call to provide an overview of the study, requirements for research participation, and review eligibility for the study (**Appendix A**). The study candidates and guardians will be informed whether they may be eligible for the study, and if so, a virtual informed consent

HRP-503a - TEMPLATE - Interventional Research Protocol 1.1.21 Protocol Title: Gut microbiota and hyperphagia in PWS Protocol Version Date: October 7, 2022

interview with the research team will be scheduled **(Appendix B).** Female candidates will be given two pregnancy test kits (Rapid Detection Pregnancy Test, Clearblue, Geneva, Switzerland) via mail and will perform the test on the day of the fMRI.

**INFORMED CONSENT AND ELIGIBILITY SCREENING PART 2.** The informed consent process will be conducted virtually through Rutgers Zoom, which is HIPPA protected. The study coordinator will explain the rationale, aim, expected outcomes significance of the research, the experimental procedures, what is required from the participants, and the benefits and risks associated with the study. Informed consent form and consent for health information release will be signed during the interview using DocuSign, a HIPPA compliant platform during the interview (**Appendix B**). The study candidates will receive copies of both signed documents. Upon completing these documents, the study coordinator will ask some additional questions regarding their medical history and other conditions to establish eligibility. Candidates will perform and present proof of a negative pregnancy test result the first study session.

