## B. Data Points

- Gut microbiota composition: fecal samples will be collected at weeks 0 and 4.
- fMRI scans will be completed at baseline and end of intervention.
- Blood parameters (satiety hormones and inflammatory markers) at minutes 0, 30, 60, 120, 180, and 240 post-meal at week 0 and week 4.
- Appetite and physical activity questionnaires at weeks 0 and 4.
- Calorie count calculated via 24-h food recall on MyFitnessPal at weeks 0 and 4.

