## B. Subject Screening

## Inclusion Criteria

- Aged between 18-45 (inclusive)
- Confirmed PWS with genetic testing or documented ICD9/10 coding for hyperphagia
- No growth hormone treatment in the previous 6 months
- Body weight < 300 lbs.
- Exclusion Criteria
  - History of other gastrointestinal disorders such as small intestinal bacterial overgrowth, celiac disease, inflammatory bowel disease, or irritable bowel syndrome.
  - Pregnancy or breastfeeding
  - Prior gastrointestinal or bariatric surgery
  - Immunocompromised e.g., cancer treatment, bone marrow/organ transplant, immune deficiency, poorly controlled HIV/AIDS, prolonged use of steroids or other immunosuppressant medications
  - Antibiotic administration in the previous 30 days
  - o Administration of pre/probiotic supplements or antibiotics.
  - Growth hormone administration in the previous 6 months
  - Have access to a smartphone, tablet, computer, or other qualifying internet-enabled device and be able to follow instructions.

HRP-503a - TEMPLATE - Interventional Research Protocol 1.1.21 Protocol Title: Gut microbiota and hyperphagia in PWS Protocol Version Date: October 7, 2022

- o Individuals who are not proficient in English

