## 4.7 Risks of Harm/Potential for Benefits to Subjects

## A. Description of Risks of Harm to Subjects

Reasonably Foreseeable Risks of Harm

Measuring fasting blood glucose during the study both involves a finger prick that pierces the skin. There may be a bruise, bleeding, or infection, at the place where the skin is pierced. However, infection is rare. Collecting fecal samples at home may impose inconvenience for the participants and their families. Participants taking NBT-BN108 may experience gastrointestinal symptoms (e.g. abdominal pain/discomfort, constipation, or bloating). These discomforts are

minor and should not last longer than a few hours. This product is low in digestible and simple carbohydrates and may reduce food intake.

There are no known health risks associated with the magnetic field produced by this 3.0T scanner in healthy adults. The FDA has indicated that they consider MR imaging on machines up to 4.0T to pose no risk (https://www.fda.gov/medical-devices/cdrh-research-programs/magnetic-resonance-imaging-mri-safety-and-effectiveness). Sammet (2016) provides discussion of MRI safety issues, each of which can be avoided with proper management. These include:1) attractive forces and torque caused by the magnet, 2) thermal effects caused by the radiofrequency fields, 3) peripheral nerve stimulation due to switching gradients, 4) hearing damage caused by the acoustic noise of the gradient system, 5) questions of risk for a fetus, 6) claustrophobia and other discomforts. These are briefly detailed below.

*Attractive Forces*: Ferrous material can be pulled toward the magnet, causing injury to a subject. These forces can cause metallic implants to be attracted to the magnet. The magnet can erase credit cards and other types of swipe cards.

Thermal Effects: The radiofrequency field can cause heating of ferrous material that are in the field, this is a concern for metal implants, and tattoos on the skin that specifically contain metal (iron).

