## E. Minimizing Risks of Harm

Participants will be provided with oral and written instructions and supplies to collect fecal samples at home without direct physical contact with the specimens throughout the process (Appendix D). The specimens will be stored in a sealed container, a leak-proof secondary package (a sealable plastic bag lined with absorbent pads) and an outer package (e.g. a shipping box). Participants are not required to store the samples at home; they will mail the specimens to the research team using the shipping supplies provided.

To minimize adverse effects due to NBT-NM108, they will also be advised to drink enough fluids throughout the study (approximately eight 8-ounce glasses of fluid a day including the amount of water taken together with NBT-NM108) to avoid constipation. Participants will be asked to monitor potential adverse events daily. If participants report an adverse event, a member of the study team will contact them to ask follow-up questions about the degree of severity (mild, moderate, or severe) and the frequency of the adverse events. The study physician (PI [name]) will assess the adverse events and, if necessary, she will instruct the participants to discontinue treatment.

Measuring fasting blood glucose during the study both involves a finger prick that pierces the skin. There may be a bruise, bleeding, or infection, at the place where the skin is pierced. However, infection is rare. To minimize adverse effects, venipuncture will be done by a certified venupuncturist.

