## 6.3 Data and Safety Monitoring

## A. Data/Safety Monitoring Plan

A Data and Safety Monitoring Board (DSMB) will approve the protocol before the study is initiated, and after 30% of the participants complete 14 days of the intervention to review study progress including recruitment, retention, adherence, adverse events and study outcomes, as well as to ensure that participant safety is addressed adequately. Reports of adverse events will be used to assess the safety of the study.

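### No gastrointestinal symptom record is scheduled before the first muffin, so the single-arm safety review cannot cleanly separate pre-existing symptoms from new or worsened ones

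*Combined protocol and SAP*

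**What the plan says.** **How side effects are recorded.** Section 1.7 A supplies the diary together with the four-week muffin regimen: "Participants will be given a supplement diary to keep track of consumption of muffins along with potential side effects". The form itself is Appendix H. Section 4.7 E adds that "Participants will be asked to monitor potential adverse events daily", without a start date.

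**What is expected.** Section 4.7 A says that people taking the product "may experience gastrointestinal symptoms (e.g. abdominal pain/discomfort, constipation, or bloating"). It gives no rate.

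**What is measured at Week 0.** Section 1.3 B lists stool, fMRI, blood, food recall, and "Appetite and physical activity questionnaires at weeks 0 and 4". Section 1.3 D adds weight. No gastrointestinal symptom item appears in either list or in the description of baseline testing in 1.3 A.

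**What else is known before treatment.** The coordinator takes a history after consent: "the study coordinator will ask some additional questions regarding their medical history and other conditions to establish eligibility". Section 4.1 B excludes "History of other gastrointestinal disorders such as small intestinal bacterial overgrowth, celiac disease, inflammatory bowel disease, or irritable bowel syndrome". Section 5.1 allows review of the medical record.

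**What happens to a report.** Under 4.7 E, staff contact the participant to "ask follow-up questions about the degree of severity (mild, moderate, or severe) and the frequency of the adverse events", and the study physician then assesses the event. Section 6.3 A states: "Reports of adverse events will be used to assess the safety of the study". The DSMB reviews adverse events after 30% of participants have completed 14 days.

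**The concern.** The symptoms named as possible product effects are non-specific and also occur in people who take no supplement. With no control arm, the only available comparator is each participant's own state before treatment. Each listed outcome has a Week 0 value, but the body text gives no equivalent for side effects. Daily prompting about symptoms appears to begin when the fibre does, so more symptoms may be noticed and written down simply because someone is now asking.

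What is at stake is how the safety data are read. The physician and the DSMB may see constipation in the diary without a comparable record of whether it was already there. A side-effect rate later quoted from the diary would mix background symptoms with product effects. A prospective baseline record cannot be made once dosing has begun. Later recall is a weak substitute, especially as section 4.5 D expects participants to lack decision-making capacity (although it also provides for individual assessment).

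**Working it through.** The plan states no side-effect rate, tolerability threshold or power calculation (1.5), so there is no figure to reproduce. The check has two parts.

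**1. Is there any like-for-like baseline?**
- Diary (1.7 A): linked to muffin consumption. No pre-treatment use is stated.
- Daily monitoring (4.7 E): no start date.
- Week 0 data points (1.3 B and 1.3 D): no gastrointestinal item.
- Screening history (1.3 A): taken for eligibility, content unspecified, not daily and not graded.
- Exclusions (4.1 B): cover gastrointestinal disorders, including irritable bowel syndrome. Isolated constipation or bloating is not named.
- Event follow-up (4.7 E): severity and frequency. It does not ask whether the symptom predates the product.
- Relatedness wording (6.3 B): only for life-threatening or fatal serious events.

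The pre-treatment information is therefore partial, and none of it matches the diary.

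**2. How much could background symptoms contribute?** Let *b* be the proportion with at least one listed symptom in four weeks without the product. The documents give no value, so 10% to 40% is assumed. From the documents, n = 10 (1.5, 4.3), and the DSMB look is at 0.30 × 10 = 3 participants.

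- Expected background reporters among 10: 10*b*.
- Chance of at least one among 10: 1 − (1 − *b*)^10.
- Chance of at least one among 3, applying the four-week rate: 1 − (1 − *b*)^3.
- The same over 14 of 28 days, if onset is at a constant rate: 1 − (1 − *b*)^(3 × 14/28) = 1 − (1 − *b*)^1.5.
- If the product independently causes symptoms in a proportion *p*, the crude on-treatment rate is 1 − (1 − *b*)(1 − *p*), which exceeds *p* by *b*(1 − *p*). Here *p* = 20% is assumed.

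| *b* (assumed) | Expected of 10 | At least one of 10 | At least one of 3, four-week rate | At least one of 3, 14 days at constant rate | Crude rate if *p* = 20% | Excess over *p* |
|---|---|---|---|---|---|---|
| 10% | 1 | 65% | 27% | 15% | 28% | 8 points |
| 20% | 2 | 89% | 49% | 28% | 36% | 16 points |
| 30% | 3 | 97% | 66% | 41% | 44% | 24 points |
| 40% | 4 | 99% | 78% | 54% | 52% | 32 points |

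The last column is an error only if crude on-treatment symptoms are presented as caused by the product. Sampling error is large in any case: 3 of 10 has an exact 95% interval of 6.7% to 65.2%.

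**How much would a short baseline catch?** If symptoms are episodic with a constant rate, a baseline of *d* days detects 1 − (1 − *b*)^(*d*/28). At *b* = 20% this is 2.4% for 3 days, 5.4% for 7 days and 10.6% for 14 days. A symptom present every day would be caught by any of these.

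**The case against.** A reader might infer that the trial has a tolerability result and that it is biased. The documents do not support that. Tolerability is not an endpoint (1.3 D), an outcome measure (1.6 B) or part of the analysis plan (6.1). Section 6.4 C plans publication of findings but no side-effect rate.

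A reader might also infer that every diary symptom is counted as a product effect, or that symptoms must rise from none to some. Neither follows. The plan speaks only of potential side effects and sends reports to a physician for individual assessment. An unmeasured baseline is missing, not zero. At a 10% background rate there is still a 35% chance that none of the 10 reports a background symptom.

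Other points stand in part:
- History, record review and the exclusions do give some baseline information and should lower the background rate. They do not give a graded daily record to set beside the diary.
- Appendix H (diary) and Appendix F (DSMB) are not in the text reviewed. Either could contain a baseline page or an attribution rule.
- Over-recording errs towards caution, and the automatic suspension in 6.3 B concerns only related life-threatening or fatal events.
- A few baseline days would miss most episodic symptoms. This limits the fix but does not remove its value for persistent complaints such as long-standing constipation.

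**Conclusion.** The point holds as a minor gap in safety data collection. On the body text, pre-existing gastrointestinal symptoms cannot be cleanly separated from new or worsened ones in the reports that reach the physician and the DSMB, and a side-effect rate taken from the diary could be too high. The possible error runs towards making the product look less well tolerated than it is.

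Its size is unknown. The 1 to 4 background reporters per 10, and the 8 to 32 point excess, rest on an assumed 10% to 40% background rate that is not adjusted for the exclusions. The excess also assumes a 20% product effect, independence, and crude reporting that the plan does not propose. The conclusion further assumes that diary use starts with the product, which is the natural reading of 1.7 A but cannot be confirmed without Appendix H. Gut microbiota composition and the listed secondary outcomes are not affected.

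**What to change.** - **Section 1.7 A:** have the participant, with the guardian, complete the same Appendix H symptom page, with severity, for a stated number of days in the existing baseline period before the first muffin. Section 1.3 A already places baseline testing and stool collection there. The length of that period is not given, and 1.3 C allots 28 days in total, the same as the four-week intervention, so the number of days needs to be written in and 1.3 C aligned with it.
- **Section 6.3:** show all on-treatment symptoms, flag those that are new or more severe than at baseline, and give symptom-days per diary day before and during treatment. Note beside the table that a short baseline mainly captures persistent symptoms, so an unflagged background of episodic ones remains.
- If Appendix F or Appendix H already provides for this, a cross-reference in the body text is enough.

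The cost is a few added diary days for participant and guardian and an extra column in the safety table. No extra staff, visit or procedure is needed. The baseline rates will be imprecise with 10 participants and few days, and should be described as such.

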## B. Drug/Device Accountability and Storage Methods

NBT-NM108 will be manufactured by Safe Sterilization USA ([name]), which is an FDA FSMA compliant GMP/NSF certified third party toll manufacturing facility and supplied by Notitia Biotechnologies. NBT-NM108 will be prepared into muffins by a ready to eat manufacturer and provided to participants.

## 1.8 Specimen Collection

## A. Primary Specimen Collection

## Types of Specimens:

- Stool. Each participant will be provided with kits to collect fecal samples at home in Week 0 and Week 4. The fecal sample collection kit has been cleared by FDA for at-home use. Instructions and supplies will be provided to collect these samples at home (Appendix D).
- 2) Blood. Venous blood draws (10 ml each) will be taken during the baseline and Week 4 post-intervention meal tests (T=0, 30, 60, 120, 180 and 240 min of each test) at IFNH by qualified professionals including phlebotomists, registered nurses and physicians.
- Annotation: Data to be annotated or associated with each specimen will include participant code, age, sex, ethnicity, medical history, and medications.

## Transport:

- Stool. Participants will return the samples by mailing them to the research team in prepaid shipping boxes. They will either schedule a FedEx pickup or drop off the package at a local FedEx office. The shipping packages are DOT (Department of Transportation) and IATA (International Air Transport Association) compliant.
- 2) Blood. The samples will be processed and analyzed by [name] lab located at the IFNH.

